9.2.1.7 Important Protocol Deviations

An important protocol deviation (IPD) is a deviation that may significantly affect the completeness, accuracy, or reliability of the study data or that may significantly affect a subject's rights, safety, or well-being. IPD rules will be developed and finalized before database cut/lock.

The protocol deviations that should be considered as potential IPDs include, but are not limited to:

- Subject was enrolled in the study despite the violation of inclusion/exclusion criteria
- Subject was less than 80% compliant with study drug for non-safety reasons
- Subject received prohibited concomitant medications
- Subject received the wrong treatment or incorrect doses
- Subject remained in the study despite meeting withdrawal criteria

Occurrence of any of these events should be considered as potential IPDs, but a blinded team should categorize them as IPDs only if they have the potential to significantly affect the completeness, accuracy, or reliability of the study data or that may significantly affect a subject's rights, safety, or well-being.

IPDs (from the clinical database or from the site deviation log) will be summarized descriptively based on the FAS and presented by treatment group and overall. Additionally, IPDs will be provided in an individual subject data listing.

9.2.2 Efficacy Analysis

Unless otherwise specified, all efficacy analyses described in this section will be based on the FAS and presented by treatment group. The study baseline will be used to calculate the change from baseline for continuous efficacy endpoints.

9.2.2.1 Analysis of Primary Variable

9.2.2.1.1 Definition of Variable

The primary efficacy variable is the absolute change from baseline in MRI global chest score at Week 48.

MRI Chest Scores: MRI scans will be assessed semi-quantitatively via a standardized chest MRI scoring system^{8,9}. Each subject will have 6 lobes scored with the lingula treated as a separate lobe. The scoring parameters, score aggregation, and global score calculations are described as below.

After scans are reviewed, MRI scores will be captured using the following 7 scoring parameters for each of the 6 lobes:

1. Bronchiectasis / Wall thickening
2. Mucus plugging
3. Abscesses / Sacculations
4. Consolidations
5. Special findings
6. Mosaic pattern
7. Perfusion abnormalities

Scores assigned to each parameter:

- 0 = normal
- 1 = < 50% of lobe involved
- 2 = \geq 50% of lobe involved

The primary variable of MRI Global Chest Score is defined as:

- MRI Global Score = Sum of parameters 1 – 7

9.2.2.1.2 Primary Analysis

The primary analysis will be performed using Bayesian methods. Specifically, the actual Bayesian posterior probability of LUM/IVA being superior to Placebo in the MRI global chest score at Week 48 will be calculated using a vague normal prior distribution. Bayesian summary statistics including the Bayesian posterior mean difference and corresponding 95% credible intervals will also be provided.

In addition, descriptive summary statistics for both between treatment arm difference and within-treatment change at Week 48 will be presented. Descriptive summary statistics including number of subjects (n), mean, median, SD, minimum, and maximum, along with the corresponding 95% CIs will be provided.

9.2.2.2 Analysis of Secondary Variables

9.2.2.2.1 Definition of Variables

Lung clearance index (LCI): LCI assessments are derived from N2-multiple-breath washout (MBW) testing. LCI_{2.5} represents the number of lung turnovers required to reduce the end tidal inert gas concentration to 1/40th of its starting value, [REDACTED]

[REDACTED] Refer to Section 11.4.2 of the CSP for details.

Body mass index (BMI): the BMI at each visit is calculated using the weight and height at each visit as follows:

$$\text{BMI} = \text{Weight (kg)} / [\text{Height (m)}]^2$$

BMI z-score: the BMI score, adjusted for age and sex, will be referred to as BMI-for-age z-score (BMI z-score). The BMI z-score will be calculated by using Centers for Disease Control and Prevention (CDC) growth charts⁷, with the age (in months) used for the calculation defined in [Appendix A](#).

Stature z-score: stature, adjusted for age and sex, will be referred to as stature-for-age z-score (stature z-score). The calculation of stature z-score is similar to that of BMI z-score.

Weight z-score: weight, adjusted for age and sex, will be referred to as weight-for-age z-score (weight z-score). The calculation of weight z-score will be exactly the same as stature z-score.

9.2.2.2.2 Analysis Method

Both within-treatment arm change and between treatment arm difference will be analyzed for secondary variables, subject to the considerations described below.

Absolute change from baseline in LCI_{2.5} through Week 48:

Analysis of within-treatment arm change will be based on descriptive summary statistics. The change from baseline to the average of all post-baseline measures at scheduled visits through Week 48 (defined as the average of Week 12, 24, 36, 48) will be used for this analysis.

Descriptive summary statistics include number of subjects (n), mean, median, SD, minimum, and maximum, along with the corresponding 95% CIs will be provided.

If the LUM/IVA treatment group or the placebo group demonstrates a within-treatment arm change with 95% CI excluding 0, and the variability of this variable is within expectation, the analysis of between-treatment difference may also be performed based on the descriptive summary statistics with the corresponding 95% CIs.

In addition, the summary of raw values and the absolute change from baseline at each post-baseline visit up to Week 48 will be provided.

Absolute change in Weight z-score from baseline at Week 48:

[figure not shown]
Absolute change in Stature z-score from baseline at Week 48:

[figure not shown]
Absolute change in BMI z-score from baseline at Week 48:

Analyses of within-treatment arm change will be based on descriptive summary statistics. The change from baseline at Week 48 will be used for this analysis. Descriptive summary statistics including number of subjects (n), mean, median, SD, minimum, and maximum, along with the corresponding 95% CIs will be provided.

If the LUM/IVA treatment group or the placebo group demonstrates a within-treatment arm change with 95% CI excluding 0, and the variability of this variable is within expectation, the analysis of between-treatment difference may also be performed based on the descriptive summary statistics with the corresponding 95% CIs.

Additional summary of raw values and absolute changes from baseline at each post-baseline visit up to Week 48 will also be provided.

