Given the intent to try to demonstrate efficacy with respect to MRI chest score and LCI, which are still endpoints under evaluation in this age group, the use of placebo in Part 1 (48-week Placebo-controlled Period) is necessary in order to provide a robust assessment. It is considered justified since all subjects within the relevant country are expected to be recruited before LUM/IVA is approved in this age group or is available commercially. The placebo or active drug will be added to subject's current standard of care, and no therapies are required to be withdrawn. Therefore, no subject will be considered disadvantaged by the use of placebo, and all will have the potential to benefit in the rollover study when they will receive LUM/IVA. Furthermore, this study is randomized 2:1, with twice as many subjects being on active therapy.

Exploration of the efficacy of LUM/IVA over the course of Part 2 (48-week Open-label Period) in this younger CF population will continue to provide information about disease progression and the potential for disease modification by early CFTR-targeted intervention.

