#### 12.3.3.3 Analysis of Secondary Endpoints

- **Absolute change from baseline in LCI2.5 through Week 48**

The secondary endpoint of absolute change in LCI2.5 from baseline through Week 48 will be analyzed using descriptive summary statistics for both between treatment arm difference and within-treatment arm change. The change from baseline to the average of all post-baseline measures at scheduled visits will be used for this analysis. Additional summary of changes from baseline at each post-baseline time point (at Week 12, Week 24, Week 36, and Week 48) will be provided in a similar way.

[figure not shown]
Descriptive summary statistics including number of subjects, mean, median, SD, minimum, and maximum, along with the corresponding 95% CIs from the descriptive summary statistics will be provided.

[figure not shown]
- **Absolute change from baseline in weight-for-age z-score at Week 48**

- **Absolute change from baseline in stature-for-age z-score at Week 48**
- **Absolute change from baseline in BMI-for-age z-score at Week 48**

For the absolute change from baseline at Week 48, the secondary endpoints above will be analyzed using descriptive summary statistics for both between treatment arm difference and within-treatment arm change. Additional summary of changes from baseline at each post-baseline time point (based on the actual time point of data collection for each of these secondary endpoints) will be provided in a similar way.

Descriptive summary statistics including number of subjects, mean, median, SD, minimum, and maximum, along with the corresponding 95% CIs from the descriptive summary statistics will be provided.

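### The SAP makes the between-arm comparison of all four secondary endpoints depend on a within-arm result, although the protocol plans it unconditionally

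*SAP*

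**What the plan says.** Protocol section 12.3.3.3 says that LCI2.5 "will be analyzed using descriptive summary statistics for both between treatment arm difference and within-treatment arm change". For the three growth measures it says that "the secondary endpoints above will be analyzed using descriptive summary statistics for both between treatment arm difference and within-treatment arm change". Both statements come with 95% CIs and neither carries a condition. The synopsis repeats the plan for LCI2.5.

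SAP section 9.2.2.2.2 opens by announcing both analyses, but "subject to the considerations described below". The consideration is that if either arm "demonstrates a within-treatment arm change with 95% CI excluding 0, and the variability of this variable is within expectation", then "the analysis of between-treatment difference may also be performed based on the descriptive summary statistics with the corresponding 95% CIs". This appears once for LCI2.5 and once after the weight, stature and BMI z-score headings. The readable text neither says what variability is expected nor gives a reason for departing from the protocol.

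The primary endpoint has no such condition. In SAP section 9.2.2.1.2, "descriptive summary statistics for both between treatment arm difference and within-treatment change at Week 48 will be presented".

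**The concern.** A change within one arm is not a treatment effect: it mixes any drug effect with growth, disease progression and drift. The condition can therefore fail in both directions. If the arms move modestly in opposite directions, neither arm's CI need exclude 0 although the arms differ. If both arms drift together, the condition is met although the drug does nothing.

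The rule also leaves a choice to be made after unblinding, because the variability criterion is undefined and the comparison stays optional even when the criterion is met.

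This sits badly with the reason given for having a placebo arm. Protocol section 9.3.1 says: "Given the intent to try to demonstrate efficacy with respect to MRI chest score and LCI" (endpoints it describes as still under evaluation at this age), "the use of placebo in Part 1 (48-week Placebo-controlled Period) is necessary in order to provide a robust assessment". For LCI the SAP then makes the placebo comparison optional. At stake is whether the report shows randomised contrasts for some secondary endpoints and only single-arm changes for others, with the choice driven by the data and the contrasts shown too large on average.

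**Working it through.** **Inputs from the documents.** Allocation 33 LUM/IVA and 17 placebo, dropout 10% (Protocol 12.1). Primary-endpoint design values: placebo change 3.0, SD 5.0, LUM/IVA threshold about 1.66 (same section). No SD or effect is given for the secondary endpoints, and SAP 6.2 states that no formal sample size calculation was done.

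**Reproducing the plan's own figure, to fix the evaluable numbers.** With a vague prior the threshold is 3.0 − z(0.80) × 5 × √(1/n₁ + 1/n₀).
- 30 and 15 evaluable (33 × 0.9 = 29.7; 17 × 0.9 = 15.3): 3.0 − 0.842 × 1.581 = 1.669, or 1.656 with a t quantile on 43 df.
- 33 and 17 evaluable: 1.744.

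The stated 1.66 matches 30 versus 15, so those are the main numbers below.

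**Model.** Normal changes with SD 1 in each arm and at least 400,000 simulated trials per scenario. The contrast counts as shown if either arm's one-sample t 95% CI excludes 0; its own interval is the pooled two-sample t 95% CI. The variability criterion is taken as met and the optional wording as always acted on.

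**True difference 0.6 SD, 30 versus 15** (reversing all signs gives the same results):

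| LUM/IVA, placebo change | Contrast shown | Mean shown difference | CIs excluding 0 that are not shown |
|---|---|---|---|
| −0.6, 0 | 89% | 0.64 | 1.7% |
| −0.5, +0.1 | 77% | 0.67 | 5.7% |
| −0.4, +0.2 | 61% | 0.73 | 12.9% |
| −0.3, +0.3 | 48% | 0.80 | 20.5% |
| −0.2, +0.4 | 43% | 0.83 | 22.5% |
| −0.1, +0.5 | 49% | 0.80 | 17.7% |
| 0, +0.6 | 60% | 0.75 | 10.2% |
| +0.2, +0.8 | 85% | 0.65 | 1.3% |
| +0.4, +1.0 | 98% | 0.61 | 0.1% |
| −0.9, −0.3 | 99.8% | 0.60 | about 0% |

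For the first seven rows, the contrast is withheld in 11% to 57% of trials. Inflation runs from 0.636/0.6 − 1 = 6% to 0.832/0.6 − 1 = 39%. With 33 versus 17 the same splits give 8% to 53% withheld and 4% to 34% inflation, and 1% to 21% of the CIs that exclude 0 are not shown. Coverage of the shown intervals stays at 94% to 96%.

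**Primary-endpoint design scenario borrowed in SD units.** 1.66/5 = 0.332 and 3.0/5 = 0.60, a true difference of 0.268. The contrast is shown in 75.7% of trials (withheld in 24%), with mean shown difference 0.301 (12% inflation); 1.4% of CIs excluding 0 are not shown.

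**No treatment effect, equal drift in both arms:**

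| Drift (SD) | Contrast shown | Coverage of shown 95% CI |
|---|---|---|
| 0 | 10% | 67% |
| 0.2 | 28% | 85% |
| 0.3 | 48% | 91% |
| 0.5 | 86% | 94% |

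The 10% agrees with 1 − 0.95² = 9.75%. In that row a shown CI wrongly excludes 0 in 0.097 × (1 − 0.673) = 3.2% of all trials, against 5% if every contrast is reported. Type I error is therefore not inflated.

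**Four endpoints together (illustrative only).** Assume one common correlation between 0 and 0.6. With no change anywhere, at least one contrast is shown in 27% to 34% of trials; independence gives 1 − 0.95⁸ = 34%. With −0.3/+0.3 on every endpoint, some but not all four are shown in 59% to 88%.

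**The case against.** The strongest reply is that little is lost. The study is exploratory, and the protocol itself calls these analyses descriptive because power is insufficient. The primary contrast is unconditional. The SAP is to be finalised before Part 1 unblinding, and the protocol leaves analysis details to it. The SAP still gives n, mean, SD and 95% CI for each arm, so a reader can rebuild an unadjusted difference; no data are suppressed. All of that stands, and it keeps the point below a threat to the trial's main conclusion. It does not justify the condition: if nothing is being tested, there is no reason to screen estimates by significance, and the protocol's explicit plan is more than a detail left open.

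A second reply is that the larger figures come from arms moving in opposite directions or one arm not moving. That is correct. With both arms moving strongly the same way the selection effect is negligible, as the last rows of the first table show. The four-endpoint figures are also rough, since BMI is calculated from weight and stature and equal correlations are unlikely.

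A third reply concerns the reading. The SAP does not literally say that the comparison is made in no other case; that follows from the qualifying clause together with the conditional sentence. Likewise, applying the single growth paragraph to weight and stature as well as BMI is an inference, though it matches the protocol's joint treatment of the three.

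**Conclusion.** The concern holds. The protocol commits to four between-arm differences; the SAP makes each conditional on a within-arm result, adds an undefined variability criterion, and leaves the comparison optional even then. This rests on the text and needs no simulation.

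The size depends on within-arm changes that the documents do not give. Under normality and the evaluable numbers implied by the protocol, it runs from almost nothing (both arms shifting strongly the same way) to 57% of contrasts withheld and 39% inflation (modest opposite changes at a true 0.6 SD). The borrowed primary-endpoint scenario lies between, at 24% withheld and 12% inflation. The consequence is selective and, on average, exaggerated presentation of secondary results. It should be fixed before unblinding.

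**What to change.** In SAP section 9.2.2.2.2, delete both conditional paragraphs (the one for LCI2.5 and the one for the z-scores) and the qualifying clause in the opening sentence. Put in their place: for each secondary endpoint, the between-treatment difference and its 95% CI will be provided whatever the within-arm results. Keep the within-arm summaries as supportive. If variability proves larger than expected, comment on it in the report and do not withhold the contrast.

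This restores agreement with Protocol section 12.3.3.3. It costs a wording change and four table rows, and needs no new data.

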9.2.3 Safety Analysis

Unless otherwise specified, all safety analyses of Part 1 analysis will be based on data from the Part 1 TE period for all subjects in the Safety Set. Subjects will be analyzed according to the treatment they actually received in the study Part 1. For subjects who have received study drug from more than one treatment, i.e. received both LUM/IVA and Placebo study drug, the treatment group allocation will be the LUM/IVA.

The overall safety profile of study drug will be assessed in terms of the following safety and tolerability assessments:

- Treatment-emergent adverse events (TEAEs)
- Clinical laboratory values
- Vital signs
- Ophthalmologic examinations (OEs)
- Physical examinations (PEs)

Only descriptive analysis will be performed for safety, and no confidence interval will be computed.

9.2.3.1 Adverse Events

For analysis purposes, AEs will be classified as pre-treatment AEs and TEAEs during the Part 1 TE Period in Part 1 analysis, defined as follows:

Pretreatment AE: any AE that occurred before the first dose date of study drug (including the matched placebo)

TEAE during the Part 1 TE Period: any AE that worsened (either in severity or seriousness) or that was newly developed at or after the first dose date of study drug (including the matched placebo) through the end of the Part 1 TE period

For AEs with completely missing or partially missing start dates, if there is no clear evidence that the AEs are pretreatment or post-treatment, the AEs will be classified as TEAEs.

Details for imputing missing or partial start dates of adverse events are described in [Appendix C](#).

An overview of all TEAEs during Part 1 TE period will be summarized by treatment group and overall in the following categories:

- Number of TEAEs
- Subjects with any TEAEs
- Subjects with TEAEs by strongest relationship
- Subjects with TEAEs by maximum severity
- Subjects with TEAEs leading to study drug discontinuation
- Subjects with TEAEs leading to study drug interruption
- Subjects with related TEAEs
- Subjects with serious TEAEs
- Subjects with TEAE leading to death

The following summary tables of TEAEs during Part 1 TE period will be presented by MedDRA System Organ Class (SOC) and Preferred Term (PT) using frequency counts and percentages (i.e., number and percentage of subjects with an event), and by treatment group:

- All TEAEs
- TEAEs by strongest relationship
- TEAEs by maximum severity
- TEAEs leading to treatment discontinuation
- TEAEs leading to treatment interruption
- Related TEAEs
- Serious TEAEs
- TEAEs leading to death

When summarizing the number and percentages of subjects, subjects with multiple occurrences of the same adverse event or a continuing adverse event will be counted once, and only the maximum severity level will be presented in the severity summaries, and the strongest relationship level in the relationship summaries.

All AEs, including pretreatment AEs and TEAEs during the Part 1 TE period will be presented in an individual subject data listing based on the All Subjects Set. In addition, separate listings containing individual subject adverse event data for TEAEs leading to treatment discontinuation, TEAEs leading to treatment interruption, SAEs and all deaths will be provided separately, with a flag indicating the TEAE status for SAEs and deaths.

The AEs of special interest (AESI) of elevated transaminases and respiratory event are defined as the following.

1. Elevated transaminases

The AESI of elevated transaminases is defined by the AEs whose PTs fall into any of the following:

- Alanine aminotransferase abnormal
- Alanine aminotransferase increased
- Aspartate aminotransferase abnormal
- Aspartate aminotransferase increased
- Transaminases abnormal
- Transaminases increased
- Liver function test abnormal
- Liver function test increased
- Hypertransaminasaemia
- Hepatic enzyme increased
- Hepatic enzyme abnormal

2. Respiratory event AESI

The respiratory event AESI is defined by the AEs whose PTs fall into any of the following:

- Asthma
- Bronchial hyperreactivity
- Bronchospasm
- Chest Discomfort
- Dyspnoea
- Respiration abnormal
- Wheezing

Treatment-emergent AESIs will be summarized by treatment group in the following categories:

- Subjects with events
- Subjects with events by maximum severity
- Subjects with events leading to treatment discontinuation
- Subjects with events leading to treatment interruption
- Subjects with serious events
- Subjects with events leading to death
- Duration of events
- Time-to-onset of first event

9.2.3.2 Clinical Laboratory

For the treatment-emergent laboratory assessments during the Part 1 TE period, the observed values and change from study baseline of the continuous hematology and chemistry results will be summarized in SI units at each visit by treatment group.

The number and percentage of subjects meeting at least 1 threshold analysis criterion during the Part 1 TE period will be summarized by treatment group. The threshold analysis criteria are provided in [Appendix D](#).

In addition, a listing containing individual subject hematology and chemistry values during the Part 1 TE period will be provided with a column indicating outside reference range or not. This listing will include data from both scheduled and unscheduled visits.

9.2.3.3 Vital Signs

For the treatment-emergent vital signs measurements during the Part 1 TE period, the observed values and change from study baseline will be summarized at each visit by treatment group. The following vital signs parameters will be summarized: systolic and diastolic blood pressure (mm Hg), body temperature (°C), pulse rate (beats per minute), and respiratory rate (breaths per minute).

In addition, a listing containing individual subject vital signs values during the Part 1 TE period will be provided. This listing will include data from both scheduled and unscheduled visits.

